One systematic review showed a worldwide prevalence of childhood constipation in the general population ranging from 0.7% to 29.6%.⁴ Similar prevalence rates were reported for boys and girls. Childhood constipation continues beyond puberty in up to one third of the children followed up.⁵ Children aged 2 to 4 years seem to have a higher recurrence rate and a need for prolonged medication and support than younger infants.⁶ One follow-up study has noted increased risk of persistent constipation in children who developed constipation early in infancy and who have a family history of constipation.⁷ Another follow-up study assessing the clinical course of severe functional constipation in early childhood found that after initial success of treatment, a relapse occurred in 15% of the children within 3 years. Symptom duration of 3 months or less before referral was significantly correlated with better outcome.⁸

Medical treatment is aimed at disimpaction of the impacted faeces and restoration of regular bowel habits, which consist of passage of soft, normal stools without discomfort. The administration of laxatives is also used to achieve a normal bowel habit of passing a soft stool without pain. Even though the traditional treatment is well established and safe, for many patients it does not provide a satisfactory improvement, prompting interest in other therapeutic strategies.⁹

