4. SELECTION AND WITHDRAWAL OF SUBJECTS

4.1 Inclusion Criteria

Subjects must satisfy the following criteria before entering the study:

1. Written informed consent obtained from subject or parent/legal guardian (and assent from subject where applicable).
2. Subject must have completed the entire 12-week treatment period during the preceding study (SAG/0211PFC-1131).
3. Subject must continue to abstain from taking concomitant medication (prescribed or over-the-counter) that affects gastrointestinal motility; these medications include:
 - a. Cholinesterase inhibitors; anti-spasmodic, anti-diarrheal, anti-constipation, or prokinetic agents; laxative agents (e.g., PEG 3350), including homeopathic remedies;
 - b. Tricyclic antidepressants; or
 - c. Any medication, at the discretion of the Investigator, known to relieve or cause constipation or constipation-related symptoms, and which the Investigator, based on the medical history of the subject, suspects to be a contributing factor to the patient's chronic constipation, or may otherwise confound the evaluation of treatment response.

Exceptions: Treatment with anticholinergic agents, SSRIs, SNRIs, or MAO inhibitors is allowed if a stable dose has been used for at least 30 days prior to the Baseline Visit (of the preceding study SAG/0211PFC-1131) and not likely to change during the study.

4. Subject (and if necessary, parent/legal guardian) must be willing and able to use or administer recommended (rectal and/or oral) rescue medications if needed.
5. If subject is taking a fibre supplement (e.g., Metamucil®, PerDiem®, Fybogel), usage must have been at a stable dose not likely to change during the study.
6. Subject and his/her parent/legal guardian must be willing and able to fill out his/her own diary.

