5.5.2 Randomisation and Blinding

This study will not involve randomisation. Due to the titration aspect of the preceding double-blinded study (SAG/0211PFC-1131), bottles will not specifically identify whether they contain lubiprostone 12 or 24 mcg so as to maintain the prior blind. Dose assignment will be based on the dose they were receiving at the time of rolling over from the preceding, double-blind study (SAG/0211PFC-1131) into this safety extension study for those subjects who were randomised to receive lubiprostone during the preceding study. For subjects who received placebo during the preceding study (as identified via IXRS), assignment of dose by the IXRS will be based on subject body weight at the time of rollover to this extension study. Dose assignment will only be known in subjects who were at least 50 kg in weight at the time of randomisation in the preceding study (SAG/0211PFC-1131). All dose assignments will be handled by the IXRS and will continue to maintain blinding with respect to the treatment assignment in the preceding trial.

Most study personnel will remain blinded to doses assigned to subjects weighing less than 50 kg until the clinical database has been locked. To allow for the execution of clinical trial-related services, the following individuals will be unblinded during the study:

- External RTSM vendor
- Sponsor Quality Assurance representative
- Sponsor Pharmacovigilance representative
- External clinical supply distribution vendor

- External third party unblinded biostatistician (e.g., DSMB statistician)
- DSMB members
- Bioanalytical laboratory and third-party pharmacokinetic analyst
- Sponsor Drug Supply Management representative

Emergency unblinding by the Investigator of a subject's assigned treatment is addressed in [Section 4.6](#) of this protocol.

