8.3 Analysis of Subject Characteristics and Completion Status

Subject demographic data will be summarized by treatment group and overall with descriptive statistics. The summaries will include mean, median, standard deviation, minimum and maximum for continuous variables, and counts and percentages for each level of categorical variables.

Baseline disease status will be assessed by constipation history, baseline period assessments of the subject's evaluation of BM frequency rates, SBM frequency rates, stool consistency, bowel straining, abdominal pain, constipation severity, incontinence episodes, occurrence of large diameter stools, retentive posturing, and the health-related quality of life using the PedsQL™ questionnaires. These data will be summarized with descriptive statistics as outlined above.

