8.6.2 Efficacy Endpoints

8.6.2.1 Overall and Monthly Change from Baseline in BM and SBM Frequency

Changes from baseline in BM and SBM frequency will be analysed overall, and at each month from Months 1 through Month 9. A month is defined as a 4-week period; e.g., Month 1 is Weeks 1-4; Month 2 is Weeks 5-8; Month 3 is Weeks 9-12. The SBM frequency rate per week will be computed as specified in [Section 8.6.2.1](#). The analyses of the months will utilize the same methods as those used in the analysis of weeks.

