8.6.2.7 Overall and Monthly Change from Baseline in Constipation Signs and Symptoms

Mean changes from baseline will be generated based on subject reported data as to the degree of:

- Straining associated with SBMs;
- Stool consistency of SBMs;
- Abdominal pain associated with SBMs; and
- Constipation severity.

The following rating scales will be used:

Stool consistency: Modified Bristol Stool Form Scale (5-point scale);

Bowel straining: 0=Not at all, 1=A little, 2=Some, 3=Quite a bit, 4=Extremely

Constipation severity and abdominal pain: 0=Absent, 1=Mild, 2=Moderate, 3=Severe, 4=Very severe.

The overall change from baseline will be calculated as the baseline value subtracted from the average of all diary ratings, where the baseline value will represent the average rating during the 2-week screening period of the previous study (SAG/0211PFC-1131). The change from baseline for a week (7-day period) or month (4-week period) will also be calculated as the baseline value subtracted from the average of all diary ratings during a week or month.

Stool Consistency

The analysis of stool consistency will focus on consistency assessments associated with SBMs. The average stool consistency rating will be calculated for each month (4-week period), excluding measurements recorded within 24 hours after rescue medication intake.

Analyses will be based on the change from baseline, where the baseline value will represent the average stool consistency rating from all SBMs during the 2-week screening period of the previous study (SAG/0211PFC-1131). The van Elteren test using the change from baseline stratified by pool centre and stratified by study for the pooled group will be used.

Straining

Bowel straining will be analysed in a method similar to stool consistency.

Constipation Severity

The changes from baseline in mean constipation severity ratings at each month during Months 1 through 9 will be analysed. The change from baseline will be calculated as the baseline value subtracted from the average of all diary ratings during the given month. For these daily diary assessments, each month will be defined by 4-week intervals beginning with the day of the first dose of study medication (Day 1). For example, Month 1 will start with the daily assessment on Day 1 and end with the daily assessment on Day 29 (Week 4), Month 2 will start with the daily assessment on Day 30 and end with the daily assessment on Day 57 (Week

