8.6.2.8 Monthly SBM Response

A monthly responder is defined as a subject who is a weekly responder for 3 of 4 weeks per month. A weekly responder is defined as a subject who has a frequency rate of ≥ 3 SBMs/week and an increase from baseline of ≥ 1 SBM/week for that week. Analyses of the frequency rates of SBMs per month will be performed using the van Elteren test, stratified by pooled centres.

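### For the four symptom scales in 8.6.2.7, change from baseline in ex-placebo children includes 12 weeks of placebo, and no summary planned in the protocol separates that period from time on lubiprostone

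*Combined protocol and SAP*

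**What the plan says.** Section 8.6.2.7 defines change for the four sign and symptom scales by subtracting a baseline, "where the baseline value will represent the average rating during the 2-week screening period of the previous study (SAG/0211PFC-1131". It repeats this for stool consistency, "where the baseline value will represent the average stool consistency rating from all SBMs during the 2-week screening period of the previous study". Neither sentence distinguishes children by their treatment in study 1131.

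Section 4.1 sets the route into the extension: "Subject must have completed the entire 12-week treatment period during the preceding study (SAG/0211PFC-1131". Section 5.5.2 shows that former placebo children then start active drug: "For subjects who received placebo during the preceding study (as identified via IXRS), assignment of dose by the IXRS will be based" on body weight at rollover. The same section says that the extension is not randomised.

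For the SBM endpoints the baseline period is not stated. The responder rule in 8.6.2.8 asks for "an increase from baseline of ≥ 1 SBM/week for that week" without saying when baseline was measured. Section 8.6.2.1 refers to itself: "The SBM frequency rate per week will be computed as specified in [Section 8.6.2.1". Sections 8.6.2.2 to 8.6.2.6 point to 8.6.2.2, which names no period either. Section 8.3 speaks of a baseline period ("Baseline disease status will be assessed by constipation history, baseline period assessments") but does not place it in time.

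**The concern.** Long-term efficacy is a stated objective (section 2.1), although safety is primary. A reader of the study report will naturally take a mean change from baseline at Month 1 or Month 9 as change on lubiprostone.

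For former placebo children it is not that. Their change also contains whatever happened between 1131 screening and rollover: placebo response, regression from a screening period, and the selection involved in completing 12 weeks. There is no concurrent control from which this could be subtracted.

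Dose comparisons may be touched as well. Former lubiprostone children carry over their dose, while former placebo children are assigned a dose by weight, so the two dose groups can hold different shares of former placebo children.

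**Working it through.** **No figure of the plan to reproduce.** The only design number is the planned enrolment of 415. Section 8.1 bases it on attrition but gives no rate or target, so it cannot be re-derived. The point does not depend on it.

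**Step 1: timing, from the documents.** Baseline lies before the 12-week parent treatment period. Visit 9 coincides with parent Visit 7 (end of treatment), and a month is 4 weeks. Time from the start of parent treatment for a former placebo child:
- End of Month 1: 12 + 4 = 16 weeks, of which 12/16 = 75% on placebo.
- End of Month 9: 12 + 36 = 48 weeks, of which 12/48 = 25% on placebo.

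These are shares of time, not of effect. They show only that the placebo period is a large part of the interval, most of all in the early months.

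**Step 2: does any planned summary separate the periods?** Demographics (8.3) and the synopsis safety summaries are by treatment group and overall. Adverse events (8.5.2) are by dose group and overall. PedsQL (8.6.2.10) is by treatment arm, a term the protocol does not define. The diary endpoints in 8.6.2 name no grouping, and the van Elteren tests name strata but not the groups compared. Nothing in the protocol is split by parent-study arm, and no rollover value is defined for diary endpoints.

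**Step 3: which endpoints are reached?**
- Stated 1131 screening baseline: straining, stool consistency, abdominal pain, constipation severity.
- Baseline period not stated: BM and SBM frequency, SBM response, incontinence, large stools, toilet use, impaction, retentive posturing. For the diary endpoints the 1131 screening period is the likely reading by analogy with 8.6.2.7, but it is an inference.
- PedsQL: baseline not stated; a questionnaire is completed at Visit 9, so a rollover baseline is possible.
- Treatment effectiveness (8.6.2.9): a rating with no baseline subtracted; not affected.

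**Step 4: size in the pooled mean.** Let s be the former placebo share, d their mean change over the placebo period, e their mean change after rollover, and c the mean change from screening in former lubiprostone children. Then

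pooled change = s(d + e) + (1 - s)c,

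and s x d arose before any lubiprostone. Neither s nor d is in the documents. Assuming s = 1/3 to 1/2 (415/3 = 138 to 415/2 = about 208 children), the term is d/3 to d/2.

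For SBM frequency, if its baseline is also 1131 screening, assumed values of d give:

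| d (SBM/week) | s = 1/3 | s = 1/2 |
|---|---|---|
| 0.5 | 0.17 | 0.25 |
| 1.0 | 0.33 | 0.50 |
| 1.5 | 0.50 | 0.75 |

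**Step 5: response, illustration only.** Assume a screening rate of 1.5 SBM/week and Poisson weekly counts with mean r, unchanged by the drug. From a screening baseline a week needs at least 3 SBMs, since 1.5 + 1 = 2.5 is below 3. With p = P(count ≥ 3), monthly response (at least 3 of 4 weeks) is 4p³(1 - p) + p⁴. The last two columns show the result if the baseline inside the rule were reset to the rollover rate r.

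| r at rollover | p | Monthly, screening baseline | SBMs needed if reset | Monthly if reset |
|---|---|---|---|---|
| 2.0 | 0.323 | 10.2% | 3 | 10.2% |
| 2.5 | 0.456 | 25.0% | 4 | 4.7% |
| 3.0 | 0.577 | 43.6% | 4 | 12.9% |
| 3.5 | 0.679 | 61.5% | 5 | 6.6% |

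Under the screening baseline and no drug effect, the third column applies equally to 1131 Weeks 9-12 and to extension Month 1, so showing the two side by side exposes the carried-over part. Resetting the baseline inside the rule instead raises the bar for children who improved on placebo and gives rates that do not rise with r.

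**The case against.** The strongest reply is that the screening baseline is the right common reference. For former lubiprostone children it is the only untreated period, and it is the same for everyone. Efficacy is not the primary objective, and no comparison with placebo is specified, so the plan does not itself attribute the change to the drug. The protocol also defers detail to the SAP, whose text is not part of the supplied document, so a split by prior arm there cannot be ruled out. All this stands, and it is why the common baseline should be kept. It does not remove the need for a split: two-sided tests at 0.05 are planned, efficacy is an objective, and the protocol shows no table from which the placebo period could be recognised.

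A reader might infer more than the documents support:
- That response is measured from 1131 screening. Likely, but 8.6.2.8 does not say so.
- That every efficacy result is biased. Treatment effectiveness has no baseline, and that for PedsQL is open.
- That the protocol's own disease overview predicts improvement during the placebo weeks. The statement "Childhood constipation continues beyond puberty in up to one third of the children followed up" concerns persistence past puberty, not a 12-week window.
- That a definite number of children enter as responders before any lubiprostone. That needs an allocation ratio and a placebo response rate, and neither is given.

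**Conclusion.** The point holds for straining, stool consistency, abdominal pain and constipation severity: in former placebo children, change from baseline covers 12 weeks of placebo before the first lubiprostone dose, and no summary in the protocol separates the periods. A pooled change from screening is therefore not change on lubiprostone. For SBM frequency and response the same is probable, but the firm finding is that their baseline period is not stated.

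The size is unknown. On an assumed former placebo share of one third to one half, a third to a half of the mean placebo-period change passes into the pooled mean. For response, the illustration shows no difference between the two baselines at a rollover rate of 2.0 SBM/week and a large one at 2.5 and above. These figures rest on assumed inputs. This is a cheap improvement to a non-primary objective.

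**What to change.** In section 8.6.2 and the SAP:
1. State that the 2-week screening period of 1131 is the common baseline for the diary endpoints, including SBM frequency and response. State separately which visit is baseline for PedsQL.
2. Present all efficacy results by parent-study arm (ex-placebo, ex-lubiprostone) as well as by dose and overall.
3. For ex-placebo children, add a supplementary within-child summary of change from 1131 Weeks 9-12. Show their Month 1-9 response rates beside their Weeks 9-12 response under the same responder rule.
4. Do not report the pooled change from screening as the lubiprostone effect.

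Do not replace the baseline inside the responder rule, and do not mix two baselines in one pooled analysis; either would make the groups non-comparable.

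The cost is wording and a few tables. Subject identifiers (5.5.3) and the electronic diary (6.1.1) carry over from 1131, no visit or procedure changes, and the split can be made after database lock so that the blind is kept. It assumes that the 1131 treatment-period diary recorded the same items. The reported change in ex-placebo children will probably be smaller, and natural improvement after rollover remains uncontrolled.

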2.2.2 Efficacy

The efficacy endpoints are as follows:

- Overall and monthly changes from baseline in BM and SBM frequency rate
- Overall and monthly assessments of the average degree of, and changes from baseline in:
 - Stool consistency of SBMs
 - Straining associated with SBMs
 - Abdominal pain associated with SBMs
 - Constipation severity
- Monthly SBM Response
 - A monthly responder is defined as a subject who is a weekly responder for 3 of 4 weeks per month.

- A weekly responder is defined as a subject who has a frequency rate of ≥ 3 SBMs/week and an increase from baseline of ≥ 1 SBM/week for that week.
- Overall and monthly assessment of average treatment effectiveness rating
- Overall Health-related quality of life (PedsQL™)
- Overall and monthly change from baseline in incontinence episodes frequency (analysis performed for subset of subjects presenting with incontinence at baseline)
- Overall and monthly change from baseline in the production of large diameter stool (a stool that clogs the toilet) frequency
- Overall and monthly change from baseline in frequency of faecal impaction
- Overall and monthly change from baseline in proportion of BMs and SBMs in toilet overall
- Overall and monthly change from baseline in frequency of retentive posturing or excessive volitional stool retention

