4.2 Exclusion Criteria

Subjects who meet any of the following criteria will be excluded from participating in the study:

1. Subject has current evidence of untreated faecal impaction.
2. Subject has experienced an adverse event during the SAG/0211PFC-1131 study which the Investigator considers to be clinically significant and would limit the subject's ability to participate in the trial.
3. Subject has had a significant change in their medical status, newly diagnosed and uncontrolled cardiovascular, liver or lung disease, neurologic or psychiatric disorder, or other systemic disease, which the Investigator considers to be clinically significant and would limit the subject's ability to participate in the trial.

4. Subject has developed an abnormal laboratory test (haematology, urinalysis, or blood chemistry), which in the Investigator's opinion is clinically significant and would limit the subject's ability to participate in the trial.
5. Subject (female of childbearing potential) has a positive pregnancy test, refuses/is unwilling to undergo pregnancy testing, and/or does not agree to use protocol-specified contraceptive measures for the duration of the study.
6. Subject demonstrated non-compliance with study protocol (i.e., dosing schedule, visit schedule, diary completion, or study procedures) during the SAG/0211PFC-1131 study.

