6.3 Safety Evaluations

The following safety evaluations will be performed during the study to measure the safety of the study medication:

Adverse Events: AEs will be reported by the subject from the time of informed consent through the end of the follow-up period. AEs will be followed by the Investigator as determined by Sponsor or designee. Further details on AE reporting are provided in [Section 7](#). Any study medication related AEs persisting at the end of the study will be followed until resolution, or until a clinically stable endpoint has been reached.

In this study, faecal impaction and bone fractures will be captured as AEs. The events of faecal impaction will be used for the analysis of the fecal impaction frequency during the study (see [Section 8.6.2.5](#)).

Clinical Laboratory Tests: The following laboratory tests will be conducted and the appropriate Investigator shall determine the clinical significance of any out-of-range values.

- **Hematology Panel:** Hemoglobin, hematocrit, MCV, MCH, MCHC, RBC, WBC, white blood cell with absolute counts and percent differentials (neutrophils, lymphocytes, monocytes, eosinophils, basophils), platelet count.
- **Chemistry Panel:** Total cholesterol, triglycerides, glucose, total protein, albumin, alkaline phosphatase, AST, ALT, GGT, iron, LDH, total bilirubin, direct bilirubin, BUN, uric acid, creatinine, sodium, potassium, chloride, bicarbonate, calcium, phosphorus, magnesium.
- **Urinalysis:** Protein, glucose, ketones, occult blood, pH, specific gravity, color, appearance, leukocyte esterase, nitrite, bilirubin, and macroscopic examination. Microscopic examination will be done if abnormalities are present. Urine samples will be collected, when possible.

Physical Examination: Physical examinations will be conducted at various timepoints during the study. Any new post treatment findings or changes, as noted by the Investigator, will be reported as an AE.

Vital Signs:

Vital signs (including height and weight at designated visits) will be recorded during the study. Any post treatment clinically significant changes in vital signs (including weight) shall be noted by the Investigator and reported as an AE. Additional guidance regarding assessment of changes in blood pressure and heart rate are provided below.

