8.6.2.5 Overall and Monthly Change from Baseline in Frequency of Faecal Impaction

Change from baseline in faecal impaction frequency will be analysed overall, and at each month during Months 1 through 9 as described in [Section 8.6.2.2](#).

8.6.2.6 Overall and Monthly Change from Baseline in Frequency of Retentive Posturing or Excessive Volitional Stool Retention

Change from baseline in retentive posturing or excessive volitional stool retention frequency will be analysed overall, and at each treatment month during Months 1 through 9 as described in [Section 8.6.2.2](#).

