8), and Month 3 will start with the daily assessment on Day 58 and end with the daily assessment on Day 85 (Week 12). Each week will be defined by 7-day intervals beginning with the day of the first dose of study medication (Day 1).

The van Elteren test using the change from baseline stratified by pooled centre for the individual studies and stratified by study for the pooled group will be used.

Abdominal Pain

Abdominal pain will be analysed similarly to constipation severity. Summary tables for the monthly change from baseline will also be presented.

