
Did this bowel movement occur today or yesterday?
	
Today Yesterday
	
Observer only item

Please record the time of this bowel movement.
	
[spinner xx:xx]
	
Observer only item

Did your child have this bowel movement in the toilet?
	
Yes No I don't know
	
Observer only item

Did the bowel movement clog the toilet?
	
Yes No I don't know
	
Observer only item

Is your child with you right now and available to answer questions about this bowel movement?
	
Yes No
	
Observer only item

Read the description and look at the pictures to see which one best matches your bowel movement.
	
Chumpitazi et al (2010). J Pediatr. October; 157(4): 594–597.²³
 
  
	
Patient item OR Observer item

How hard did you have to push to have this bowel movement?
	
0 - Not at all 1 - A little 2 - Some 3 - Quite a bit 4 - Extremely
	
Patient only item

How much did it hurt when you had this bowel movement?
	
0 - Not at all 1 - A little 2 - Some 3 - Quite a bit 4 - Extremely
	
Patient only item

In the past 24 hours: What was the worst pain in your belly today?
	
0 - none 1 - mild 2 - moderate 3 - severe 4 - very severe
	
Patient only item

In the past 24 hours How would you rate your child's constipation severity?
	
0 - none 1 - mild 2 - moderate 3 - severe 4 - very severe
	
Observer only item

WEEKLY ASSESSMENT The following questions will be assessed each week immediately following the daily diary questions as part of the subject's diary:
		

STUDY MEDICATION	0 – not at all effective 1 – a little bit effective 2 – moderately effective 3 – quite a bit effective 4 – extremely effective	Observer only item
Over the past week, how well did your child's study medicine help?		
Over the past week, how many episodes of retentive posturing did your child have?	[continuous numeric; not applicable]	Observer only item

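### The SBM-associated abdominal pain endpoint is analysed from a daily pain rating not tied to any SBM; secondarily, the change in faecal impaction frequency has no stated baseline source

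*Combined protocol and SAP*

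**What the plan says.** **Abdominal pain.** Section 2.2.2 lists the endpoint as "Abdominal pain associated with SBMs", and Section 8.6.2.7 repeats that name in its own list. Section 8.6.2.7 puts abdominal pain on the same scale as constipation severity, 0 (absent) to 4 (very severe). Its method is one sentence: "Abdominal pain will be analysed similarly to constipation severity". For constipation severity the method is to average every diary rating in the month and subtract the baseline. No restriction to SBMs is stated.

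Appendix 1 contains two pain questions:

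- A daily one, "What was the worst pain in your belly today", answered from none to very severe.
- One asked for each reported movement, "How much did it hurt when you had this bowel movement", answered from not at all to extremely.

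**Faecal impaction.** Section 8.6.2.5 states: "Change from baseline in faecal impaction frequency will be analysed overall, and at each month during Months 1 through 9". Section 6.3 gives the source, which is AE reports: "The events of faecal impaction will be used for the analysis of the fecal impaction frequency during the study". The same section starts AE collection at informed consent. The baseline disease assessments in Section 8.3 do not include impaction, and Appendix 1 has no question on it.

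**The concern.** The name of the pain endpoint and its analysis describe different quantities. A reader of the study report would take a result labelled as SBM-associated pain to describe discomfort when the child passes a stool. The analysis as written describes the worst belly pain of each day, whether or not there was an SBM. Meanwhile the per-movement pain answers would be collected from children and not analysed.

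For impaction, a change from baseline needs a count over a defined period before treatment, captured in a comparable way. The plan names a source for the on-treatment period only.

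**Working it through.** **Step 1. Match the pain endpoint to a diary item.**

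| Feature | Plan for abdominal pain (8.6.2.7) | Daily item (Appendix 1) | Per-movement item (Appendix 1) |
|---|---|---|---|
| Tied to a movement | Yes, by its name | No | Yes |
| Scale | 0 absent to 4 very severe | 0 none to 4 very severe | 0 not at all to 4 extremely |
| Averaging | All diary ratings, as for constipation severity | One rating per day | One rating per movement |
| Mentions the belly | Yes, by its name | Yes | No |

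Scale and averaging rule both select the daily item. Only the words about SBMs point to the per-movement item.

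**Step 2. Compare with the neighbouring endpoints.** Section 8.6.2.7 limits stool consistency to ratings attached to SBMs and drops those within 24 hours after rescue medication. Straining follows a similar method. Abdominal pain carries the same SBM label but neither rule.

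**Step 3. How many days in the average have no SBM?** The documents give no figure, so this is a bound. Let *s* be the number of SBMs per week. At most *s* days in a week can contain an SBM, and fewer if two fall on one day. The share of days without an SBM is therefore at least (7 − *s*)/7.

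| SBMs per week | Source of the value | Minimum share of days without an SBM |
|---|---|---|
| 1.5 | Assumption | (7 − 1.5)/7 = 79% |
| 3 | Weekly responder threshold, Section 8.6.2.8 | (7 − 3)/7 = 57% |
| 5 | Assumption | (7 − 5)/7 = 29% |

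The bound exceeds one half only when *s* is below 3.5. These are shares of days. They equal shares of ratings if the daily item is answered every day.

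**Step 4. Look for an impaction baseline.** Consent is obtained at Visit 9 (Section 6.1.2), which is also the first day of study medication (Section 3.1). AE capture in this study therefore supplies no baseline period. Section 8.6.2.5 refers to Section 8.6.2.2 for its method. That section covers incontinence, refers to itself, and gives no impaction baseline. Finally, Section 8.5.2 counts a subject with repeated episodes of an AE once. Applied to impaction, that would turn a frequency into an incidence.

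**The case against.** The best defence on pain is that the SBM label is the drafting slip. Section 6.2 groups stool consistency and straining with bowel movements, and lists abdominal pain beside constipation severity and treatment effectiveness. The scale and the averaging rule agree with that grouping. The per-movement question does not mention the belly and may capture painful defecation, so it cannot simply be relabelled abdominal pain. All of this stands and shapes the fix: the daily item keeps the abdominal pain name, and the per-movement item gets its own. It does not remove the conflict between the endpoint's name and its analysis.

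The protocol also defers detail to a SAP, and neither a separate SAP text nor the preceding study's data capture is in the document. Either could supply an impaction baseline, so that part is conditional. Neither would remove the contradiction within the protocol on pain.

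Several stronger readings are tempting but not supported:

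- *Most pain ratings come from days without an SBM.* This is certain only below 3.5 SBMs per week.
- *The impaction change can only be zero or worse.* The exclusion "Subject has current evidence of untreated faecal impaction" is applied at rollover and bars only current, untreated impaction. The baseline the plan defines for diary ratings is the screening period of the preceding study. The exclusion cannot force that earlier period to zero.
- *Section 7.2.3 would suppress impaction reports.* Sections 6.3, 7 and 8.5.2 each state that impaction is captured as an AE. That specific instruction answers the general rule on disease symptoms.
- *The incontinence endpoint measures the wrong thing.* Appendix 1 has no dedicated incontinence question and no rule defines an episode, but a missing definition is not evidence of a wrong measure.

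**Conclusion.** The pain point holds. As written, the analysis yields average daily worst belly pain under a label that says SBM-associated, and the per-movement answers go unused. The days without an SBM included in that average are at least 57% at 3 SBMs per week and at least 29% at 5. At 1.5 per week, a value not in the documents, the figure is at least 79%. These percentages show how far the label departs from the data. They do not estimate any bias in a pain score, and the daily average remains a sound measure of daily pain.

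The impaction point holds in a narrower form: on-treatment AE counts do measure impaction, but the change score cannot be calculated from the sources the plan states.

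Both are efficacy endpoints in an unrandomised extension whose primary objective is safety. The matter is worth correcting because the remedy is cheap, but it does not touch the main purpose of the study.

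**What to change.** 1. **Daily item.** Report it as *daily worst abdominal pain*, with the averaging rule already in Section 8.6.2.7, and remove the SBM wording from the name wherever the endpoint is listed.
2. **Per-movement item.** Add a separate endpoint, *pain with SBMs*, on its own not-at-all-to-extremely scale. Restrict it to SBMs and exclude ratings within 24 hours after rescue medication, as for stool consistency and straining. Only the child answers this item, so also report the share of SBMs with a rating. Confirm that the same question was asked in the preceding study's screening period before promising a change from baseline.
3. **Faecal impaction.** Name a comparable baseline capture from the preceding study, with its period. If there is none, report the on-treatment episode rate per subject-month and the percentage of subjects with at least one episode. For the rate, count repeat episodes and state that the count-once rule in Section 8.5.2 does not apply.
4. **Cross-references.** Section 8.6.2.5 should point to a section that contains a method. Section 8.5.2 sends the reader to 8.6.2.6 for impaction, while Sections 6.3 and 7 cite 8.6.2.5.

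The cost is endpoint wording, a little extra analysis and, if no baseline is found, the loss of the change form for one endpoint. The diary does not change and no new data are collected.
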